Audio recording supports precise measurement of verbal communication including duration, intensity, and patterns and is less invasive than videotaping, encouraging natural communication and maintaining privacy. Recordings can be reviewed repeatedly to verify accuracy and reliability. Limitations are (1) alteration of natural speech and behavior due to the awareness of recording and (2) inability to control for environmental factors such as noise. Research has established that NH staff do not significantly modify communication if recording is presented in a nonjudgmental manner^{60,61} and this was confirmed in the PI's

research.⁴³ The audio recording protocol is designed to measure communication in NHs⁶² and health care settings;⁶³ it was effective in the PIs research, uses measures to limit the Hawthorne effect (i.e., minimally obtrusive recording equipment), and will record each CNA during the same time periods from day to day to assure consistency.^{8,27,42-44,64,65}

Preliminary Effects Testing (Aims 2): We will test preliminary effects of app feedback on elderspeak use in audio-recorded staff communication. A cluster randomized trial will be conducted in six NHs that participate in CHATO training. We will compare the immediate and delayed-feedback control groups on elderspeak (diminutive) changes after participation in CHATO. We hypothesize that staff who receive immediate feedback will demonstrate greater reductions in use of diminutives, the most common and recognizable marker of elderspeak, compared to control group staff before they receive delayed feedback. We will validate app accuracy by comparing app results to psycholinguistic coding using our established protocols for data reduction, transcription, and coding.^{8,44,66}

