Six NHs will participate in audio recording of CNA communication before and after CHATO (see letters of support). These NHs will be randomly assigned to immediate feedback (n=3; recording with app feedback on elderspeak use) or control (n=3; recording with end of study feedback) groups. In each NH, 12 CNAs will be recruited using strategies successful in our past research such as announcing the research opportunity at staff meetings. Enrollment of 12 CNAs per NH allows for levels of attrition experienced in our prior studies. If fewer than 30 CNAs per group complete recordings, more NHs will be added. CNA volunteers (at least 30 per group) will record their communication in 2-hour care sessions on 1 day before and on 3 days after completing CHATO.

In both NH groups, 12 CNAs will be recorded for a 2-hour shift prior to participating in CHATO training (baseline). The URL link to complete the CHATO modules will be provided for the CNAs as well as other NH staff. Staff will be expected to complete the training over a 2-week period. After completion, the 12 CNAs from each NH who are participating in the app testing will be recorded again within a week of completing training (post-CHATO time 1), then approximately 1 week later (post-CHATO time 2), and finally another week later (post-CHATO time 3). Immediate feedback NH CNAs will receive the app feedback at the end of each post- CHATO recording session, while control group NH CNAs will not receive app feedback until the end of their post-CHATO time 3 recording sessions.

Each NH will provide a letter of interest, acknowledging random assignment, committing to engage staff in CHATO training, and agreeing to provide descriptive and cost data including number and types of staff and average wages. Each NH will be approved prior to participation by the KUMC IRB. NH size and census, profit status, proportion of residents with dementia, presence of a special care unit, staffing and turnover ratios, Medicare star rating, antipsychotic prescription rate, and Medicaid case mix will be collected from Nursing Home Compare and NH reports. Medicaid case mix is a measure of resident acuity or care needs that is used to determine Medicaid reimbursement rates and has been used in research to control differences in care needs across NHs.^{67,68} Participating NHs will be encouraged to engage all direct care staff, including housekeeping, dietary, and administrative staff in the training.

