CHATO is presented in three modules.^{10,70} Session 1 introduces effective versus ineffective communication. Participants identify communication issues in video vignettes. Session 2 focuses on identification and negative effects of elderspeak, using video-recorded examples. Session 3 includes strategies for improved communication based on assessment of each resident's abilities. Participants critique communication in videos and correct transcripts to eliminate elderspeak. Training is limited to three 1-hour sessions to assure feasibility in busy NHs. The modules include moderated discussion and interactive exercises that must be completed to advance through the program. This assures content fidelity and dose of the intervention. CHATO is provided to as many staff as possible to achieve facility-wide effects of reduced elderspeak.⁷⁴ The modules contain pre- and post-tests (scenario-based questions and rating of staff communication in video clips) to evaluate knowledge gain. The Modified Duke Diffusion of Innovation⁷⁵ survey provides information about CHATO participant intentions to use learned skills in practice and the likelihood for translation.

Audio Recordings. CNAs will be recorded for 2 hours on 1 day in the week before and 3 days in the 2 weeks after CHATO training. To ensure consistency, every attempt will be made to make post-CHATO recordings at the same time of day. CNAs will be permitted to turn the recording unit off when they do not wish to be recorded. Although this may limit validity of the recordings, it assures privacy and participation. Recordings will be time coded and take place during morning care when elderspeak and BPSD are most frequent.^{44,76,77} To minimize attrition, CNAs will be recruited just prior to their NH's participation in CHATO training. *A priori* randomized order for NH participation will control for historical effects. Intention-to-treat analyses will be used. The feedback group CNAs will receive automated feedback on elderspeak use after each post-CHATO recording session. The control group will receive feedback for all recording sessions after their final (third post-CHATO recording session). The Project Director will download recordings for both groups and delete them from the iPod Touch.

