Aim 1: We will demonstrate feasibility, acceptability, and validity of the SPEEKO for Elderspeak feedback app with detection model algorithm optimization with a diminutive accuracy testing benchmark of 80% or higher. App outputs will be compared to data from transcription and psycholinguistic coding, using our established protocols, to validate app reliability for diminutive detection. Also, an analysis of a CNA-completed, 10-item usability scale (The System Usability Scale) with an acceptability benchmark of 50% or higher.

Aim 2: Linear Mixed Models (LMMs) or Generalized LMMs, depending on the distribution of each outcome, will be developed to determine the impact of group assignment (feedback or no feedback) on use of elderspeak diminutives. Baseline diminutive use, group (feedback vs. no feedback), recording session (pre- and post CHAT sessions 1, 2, and 3), and interaction between intervention and session will be fitted as fixed effects. To account for clustering, each NH will be fitted as a random effect. To account for correlation due to repeated measurements, an appropriate covariance pattern will be determined from data. CNA and resident sex and CNA knowledge gain will be tested as covariates. Aim 2 will estimate variability, effect sizes, and intracluster correlation for a future larger-scale study. Sample sizes of as few as 30 in each group, or 10 CNAs on average in each NH, will achieve 80% power to detect a difference between the group means of 0.74 to 0.76 standard deviations, assuming the intracluster correlation coefficient ranging from 0.001 to 0.01 and coefficient of covariation among cluster sizes of 0.25. A two-tailed t-test was used with a significant level of 0.05 and the degrees of freedom based on the number of subjects.

Aim 3: We will use process-based costing to determine average costs for using the SPEEKO for Elderspeak feedback app, comparing costs relative to any difference determined for reductions in diminutive use in the immediate and delayed feedback groups.^{80,81}

D. Subject Criteria (See Vulnerable Populations appendix, if applicable):

1. Inclusion criteria: We will recruit CNAs who are age 18 or older, permanent employees, and fluent in English to participate. Descriptive information (age, sex, race, ethnicity, role, experience) will be used to identify CNA covariate factors predicting communication

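### The Aim 2 change contrast is not clearly tested against between-home variation: one NH random effect, ordinarily an intercept, cancels from it, and no between-NH degrees of freedom are stated

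*Combined protocol and SAP*

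**What the plan says.** Section II.B (Preliminary Effects Testing) sets the unit of allocation: "A cluster randomized trial will be conducted in six NHs that participate in CHATO training", with three NHs in each group.

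Section II.C, Aim 2, gives the model. Its fixed effects are baseline diminutive use, group and recording session, where session covers the pre-training recording and the three post-training ones, "and interaction between intervention and session will be fitted as fixed effects". The provision for NH is one sentence: "To account for clustering, each NH will be fitted as a random effect". A covariance pattern chosen from the data handles repeated measurements. No NH-by-session term, NH random slope, cluster-robust variance or denominator degrees-of-freedom rule is stated. Section V.A repeats only the model class.

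The power statement takes 30 CNAs per arm, about 10 from every home, and claims that this number "will achieve 80% power to detect a difference between the group means of 0.74 to 0.76 standard deviations". It assumes an ICC of 0.001 to 0.01 and a cluster-size coefficient of variation of 0.25, and takes its degrees of freedom from the number of subjects.

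The Aim 2 hypothesis (Specific Aims, and again in V.B) is that feedback staff reduce elderspeak more after CHATO than controls do.

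**The concern.** A larger reduction is a difference in change. With the pre recording among the session levels, that difference sits in the group-by-session interaction. An NH random intercept shifts all sessions of a home equally, so it cannot represent a home whose CNAs improve more, or less, together. The repeated-measures covariance describes sessions within a CNA and does not represent this either.

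Shared change is plausible in this design. Section II.B (Session Content) says "CHATO is provided to as many staff as possible to achieve facility-wide effects of reduced elderspeak", so uptake and reinforcement among co-workers could differ by home. If they do, the contrast is judged against CNA-level error although homes were randomised. Its p-value would be too small and its interval too narrow. The NH-level variability of change, which a larger trial would need, would also go unestimated.

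**Working it through.** **1. The plan's own figure.** Inputs from II.C: 30 CNAs per group, m = 10 per NH, CV = 0.25, ICC = 0.001 to 0.01, two-sided 0.05, 80% power.

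Design effect = 1 + ((CV² + 1)m − 1) × ICC, with (1.0625 × 10 − 1) = 9.625. This gives 1.0096 at ICC 0.001 and 1.0963 at ICC 0.01.

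The standard error of a standardised difference is √(2 × DE/30). The noncentral t on 58 df gives detectable differences of 0.739 and 0.770 SD; the normal approximation gives 0.727 and 0.757 SD. The stated 0.74 to 0.76 is therefore reproduced closely.

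**2. Why the intercept cancels.** For CNA i in home j at session k, write the random part as u(j) + w(j,k) + a(i) + e(i,k), with:
- u: NH intercept
- w: NH-by-session effect, variance s
- a: CNA effect
- e: residual, variance r

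A post-minus-pre change removes u and a and leaves w(j,post) − w(j,pre) + e(i,post) − e(i,pre). Its variance is V = 2(s + r). The share common to CNAs of one NH is ρ = s/(s + r).

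The group difference in mean change, with 3 v 3 homes of 10, has variance (2V/30)(1 + 9ρ). A model with u but no w estimates only 2V/30.

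**3. Size.** The documents give neither s nor the CNA variance. Assumptions: total variance 1, CNA variance 0.50, complete balanced data, compound symmetry. The approximate type I error of one change contrast is 2[1 − Φ(1.96/√(1 + 9ρ))]. The last column is the simulated joint 3-df group-by-session F test against CNA-level error.

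| Stable NH variance | NH-by-session s | ρ | 1 + 9ρ | Single contrast | Joint test |
|---|---|---|---|---|---|
| 0.01 | 0 | 0 | 1.000 | 5.0% | 5% |
| 0.005 | 0.005 | 0.0101 | 1.091 | 6.1% | 7% |
| 0.01 | 0.01 | 0.0204 | 1.184 | 7.2% | 9% |
| 0.01 | 0.02 | 0.0408 | 1.367 | 9.4% | 13% |
| 0.01 | 0.05 | 0.1020 | 1.918 | 15.7% | 26% |

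For example, in the third row r = 1 − 0.50 − 0.01 − 0.01 = 0.48 and ρ = 0.01/0.49 = 0.0204. Simulated single-contrast errors agree with the formula: 7%, 9% and 16% in the last three rows.

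The second row keeps total NH variance at the plan's 1% ceiling, split evenly. If all of that 1% were session-specific, ρ = 0.01/0.50 = 0.02 and the errors are about 7% (single) and 9% (joint).

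With NH-level error (4 df for one contrast, F on 3 and 12 df jointly) the simulated error is about 5% in every row.

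**4. Effect of 4 df on the power statement.** With the design effects of step 1 and 6 − 2 = 4 df, the detectable difference is 0.976 SD at ICC 0.001 and 1.017 SD at ICC 0.01. Power at the stated 0.74 and 0.76 SD is 58% and 57%. This is for a difference in group means at the plan's ICC. It comes from the df basis, not from adding an NH-by-session term.

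**The case against.** **The plan does not say intercept, and it does not name the Aim 2 contrast.** Both points are correct. An unqualified random effect for NH is ordinarily an intercept, and nothing in the text suggests more. The contrast is less certain. Baseline use is also listed as a covariate, and the power statement concerns group means, which fits an analysis of post-training sessions adjusted for baseline. On that reading the averaged group effect does carry the NH intercept, and its problem reduces to the degrees of freedom. But II.C also makes the pre recording a session level and fits the interaction, so the text supports both readings.

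**The inflation may be small.** This stands too. It is nil if NH-by-session variance is zero. A reader might infer that the standard errors are certainly too small, or that 26% is the expected error rate. The documents support neither. The 26% needs session-specific NH variance of 5%, five times the stable NH variance assumed beside it and well above the plan's ICC ceiling.

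**Shared change should be limited.** CHATO is standardised and online, and its required exercises control dose. All four recordings of a home fall within a few weeks, so calendar effects go mostly into the intercept. This lowers the likely variance but does not exclude it.

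**It is a preliminary study.** It nevertheless plans a two-sided 5% test with 80% power, and is meant to supply variability and ICC estimates for a larger trial.

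**Conclusion.** The point holds as a gap in specification with a conditional consequence. On the ordinary reading, the group-by-session contrast has no protection against change shared within an NH, and no other section repairs this.

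The type I error is 5% if NH-by-session variance is zero. It is about 6% to 7% if NH variance totals 1% and is split evenly. It is 9%, 13% or 26% for the joint test (7%, 9% or 16% for time 3 minus baseline) if NH-by-session variance is 1%, 2% or 5% of the total. These figures rest on 10 CNAs per NH, balanced complete data and a CNA variance of 50%.

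A reader might also infer that the whole Aim 2 analysis treats CNAs as the randomised units. The documents do not support that: the averaged group effect carries the NH term. What is missing there is a between-NH df rule; the only df statement, in the power calculation, counts subjects.

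**What to change.** 1. Name the Aim 2 contrast, and say whether the pre recording is an outcome level or a covariate.
2. Test that contrast against between-NH variation. The simplest way is a t-test with 4 df on NH means, either of change or of baseline-adjusted post-training values.
3. If a linear mixed model is preferred, add an NH-by-session random effect and a small-sample df correction such as Kenward-Roger. Keep the NH terms when their variance is estimated as zero. The 5% shown above was obtained with the balanced NH-level error term, not with a fitted Kenward-Roger model, which is a reason to report the NH-level test as well.
4. If a generalised mixed model is used, rely on the NH-level analysis for the test.
5. Restate the detectable difference at about 0.98 to 1.02 SD for ICC 0.001 to 0.01.

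The cost is analysis-plan wording and one model term; no new data are needed. Intervals will be wider, and six NHs will estimate the NH-by-session variance poorly.

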Our recently completed R01 clinical trial that tested Changing Talk (CHAT) communication training provides preliminary data for the proposed research. CHAT increases staff awareness of elderspeak's negative effects and guides practice in more effective communication. CHAT includes three 1-hour sessions, with replicated effects on communication in three studies among staff (N=89) and residents (N=194) in over 20 NHs.^{9,42,43} Effect sizes ranged from $\eta^2 = .35$ to $.62$ for reducing elderspeak diminutives (inappropriately intimate terms of endearment) and collective "we" pronoun substitutions, effects that were maintained over 2 months. Person- centered (vs. task-focused) communication also increased after CHAT.^{9,44} CHAT was highly rated by past participants (N=217); mean program ratings ranged from 4.5 to 4.8 on a 1(low) to 5 (high) scale.⁴⁵

The CHAT R01 demonstrated that CHAT decreases staff elderspeak and reduces resident RTC.⁹ On average, elderspeak declined from 34.6% (SD = 18.7) at baseline by 13.6 percentage points (SD = 20.00) post- intervention and 12.2 percentage points (SD=22.0) after 3 months. RTC declined from 35.7% (SD = 23.2) by 15.3 percentage points (SD = 32.4) post-intervention and 13.4 percentage points (SD=33.7) at follow-up. Linear mixed modeling determined that change in elderspeak was predicted by CHAT ($b = -12.20$, $p = .028$) and baseline elderspeak ($b = -0.65$, $p < .001$), while RTC change was predicted by elderspeak change ($b = 0.43$, $p < .001$), baseline RTC ($b = -0.58$, $p < .001$), resident communication disability, and comorbid illnesses.

We also extracted CMS NH Quality Measures (NHQM) data for use of antipsychotics for the 10 CHAT NHs for which data were available. We compared each NH's rates for two quarters before and two quarters after each participated in CHAT. The percentage of residents prescribed antipsychotics decreased by an average of 4.⁹ percentage points, from 20.7% (SD=8.5) to 15.8% (SD=9.0) after CHAT. We used state average rates for antipsychotic medication use for the same time periods to control for changes that may have occurred due to the CMS mandate and other factors.⁴⁶ State benchmarks for prescribed antipsychotics averaged 25.4% across quarters before and declined to 24.9% for quarters after CHAT, a decrease of 0.5%. The average decrease in CHAT NHs (4.9%) compared to the other state NHs (0.5%) was significant ($p=0.05$ for two-tailed t-test).⁴⁷

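### Letting the data choose the repeated-measures covariance can lift change-from-pre contrasts to about 5–8% (AIC) or 6–11% (BIC) under plausible correlations; fix it in advance, after removing the double use of baseline

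*Combined protocol and SAP*

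**What the plan says.** Section II.C, Aim 2, plans a linear or generalised linear mixed model, depending on the outcome's distribution. The fixed effects are baseline diminutive use, group, recording session (with the pre session as one level) and group by session. Nursing home is a random effect. On the within-CNA correlation it says only: "To account for correlation due to repeated measurements, an appropriate covariance pattern will be determined from data". Section V.A repeats the model family and adds nothing on the covariance.

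The design has six homes ("These NHs will be randomly assigned to immediate feedback (n=3; recording with app feedback on elderspeak use) or control (n=3"), and CNAs "will record their communication in 2-hour care sessions on 1 day before and on 3 days after completing CHATO". On power: "Sample sizes of as few as 30 in each group, or 10 CNAs on average in each NH, will achieve 80% power". The detectable difference is given as 0.74 to 0.76 SD, for an ICC between 0.001 and 0.01 and a cluster-size CV of 0.25. The level is stated too: "A two-tailed t-test was used with a significant level of 0.05 and the degrees of freedom based on the number of subjects".

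No primary contrast is named. The Aim 2 hypothesis is a larger fall in elderspeak with immediate feedback, so a change-from-pre contrast is a natural reading, but not the only one.

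**The concern.** The schedule is one recording before training and three about a week apart after it. The post sessions may well correlate more with each other than with the pre session. Compound symmetry replaces both correlations by their average. That overstates the pre-post correlation and understates the variance of change from pre.

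With about 60 CNAs, a criterion that penalises parameters will often prefer compound symmetry (2 parameters) to an unstructured matrix (10 parameters) even when it is wrong for this contrast. P-values and confidence intervals for change would then be too optimistic. Aim 2 is also meant to supply variability and effect-size estimates for a larger study, so an understated standard error would carry into that planning. And with no stated rule, two analysts could reach different p-values from the same data.

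**Working it through.** **1. The plan's own power figure.** Inputs from Section II.C: 30 per group, 10 CNAs per home, CV 0.25, two-sided 0.05, 58 df. Design effect = 1 + ((1 + CV²)m − 1) × ICC.
- ICC 0.001: 1 + (10.625 − 1) × 0.001 = 1.0096. At 0.74 SD the noncentrality is 0.74/√(2 × 1.0096/30) = 2.85 and power is 80.1%.
- ICC 0.01: the design effect is 1.0963. At 0.76 SD the noncentrality is 2.81 and power is 78.9% (80.3% by the normal formula).

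The figure reproduces to within about 1 point. It does not depend on the covariance pattern.

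**2. Pre-post correlation.** Section I.B reports for the prior trial that "elderspeak declined from 34.6% (SD = 18.7) at baseline by 13.6 percentage points (SD = 20.00" post-intervention, with a change SD of 22.0 at 3 months. If SDs are equal over time, r = 1 − SD²(change)/(2 × SD²):
- 1 − 20.0²/(2 × 18.7²) = 0.43
- 1 − 22.0²/(2 × 18.7²) = 0.31

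These are for overall elderspeak, not diminutives. The documents give no post-post correlation; 0.5 to 0.6 is assumed below.

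**3. Mechanism (equal SDs, pre-post 0.43, post-post 0.60).** Compound symmetry settles on the average correlation, (3 × 0.43 + 3 × 0.60)/6 = 0.515.
- One post session minus pre: true variance 2(1 − 0.43) = 1.14; compound symmetry gives 2(1 − 0.515) = 0.97. SE ratio √(0.97/1.14) = 0.92.
- Mean of three post sessions minus pre: true variance 1 + (1 + 2 × 0.60)/3 − 2 × 0.43 = 0.873; compound symmetry gives (4/3)(1 − 0.515) = 0.647. SE ratio 0.86.

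**4. Simulated type I error.** 30 per arm, four sessions, complete data, no home effect, saturated group-by-session means with no baseline covariate. REML fits, selection from three candidates (compound symmetry, AR(1), unstructured) or six (adding Toeplitz and the heterogeneous forms), t on 58 df, 6,000 trials per scenario, Monte Carlo SE about 0.3 points.

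| Truth: pre-post / post-post | AIC, T1 or T3 − pre | BIC, T1 or T3 − pre | AIC, mean post − pre | BIC, mean post − pre |
|---|---|---|---|---|
| 0.43 / 0.60 | 5.6–6.1% | 6.1–6.8% | 7.0% | 8.0–8.2% |
| 0.31 / 0.60 | 5.1–6.0% | 5.9–8.1% | 6.4% | 8.8% |
| 0.37 / 0.50 | 5.6–6.1% | 5.9–6.1% | 6.6% | 7.1% |
| 0.43 / 0.60, post SD 0.8 of pre | 5.6–6.1% | 6.8–8.6% | 7.0% | 9.6–11.1% |

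A second simulation, with pre-post 0.31–0.43 and post-post 0.6, gave 5.6–7.6% (AIC) and 6.6–8.7% (BIC) for single sessions, and 6.5–7.9% and 8.3–10.8% for the mean.

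In the first simulation:
- With compound symmetry (0.5) or AR(1) (0.6) true, single contrasts ran at 4.0–4.7%. The second simulation gave about 5–6% under compound symmetry.
- The 3-df interaction test stayed at 4.5–6.5% in every scenario.
- Unstructured fixed in advance gave 4.4–5.4% (single) and 4.6–5.9% (mean).

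**5. Baseline as covariate, post sessions only.** With pre-post 0.43/0.37/0.31, the variances given baseline are 0.815, 0.863 and 0.904, average 0.861. Even with compound symmetry imposed, the SE ratio for T3 is √(0.861/0.904) = 0.98. For the mean of the three it is exactly 1 with complete data. Simulated size with compound symmetry imposed: 5.3–5.8% (T3) and 4.8–5.3% (mean); 4,000 runs.

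**6. Double use of baseline.** As written, the pre-session value is both a response and a covariate. With baseline slope b, each pre residual is (1 − b) × (baseline − group mean), which goes to zero as b approaches 1. Any pattern with its own pre-session variance then has an unbounded likelihood. In a check, −2 log L fell from 593 (b = 0) to 41 (b = 0.99) to −1065 (b = 0.999999).

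**7. Cost of unstructured if compound symmetry is true.** Difference 0.74 SD, 58 versus 174 df: power 80.5% versus 81.3% at r = 0.5, and 75.2% versus 76.1% at r = 0.43.

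**8. Home variance in change.** Assume an ICC of change of 0.01 (the plan's upper ICC, applied here to change) and 10 CNAs per home. The true variance factor is 0.99 + 10 × 0.01 = 1.09. The pooled estimate averages (54 × 0.99 + 4 × 1.09)/58 = 0.997. The critical value 2.002 acts as 2.002/√(1.09/0.997) = 1.91, a size of about 6.1% even with an unstructured matrix. At ICC 0.05 it is 10.4%.

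**The case against.** The strongest reply is that the inflation depends on a contrast the plan does not name and on correlations it does not give. That stands. If baseline is kept as a covariate and only post sessions are outcomes, step 5 shows almost no problem. The prior-trial SDs concern a different measure, and the 0.31 comes from 3 months, whereas these recordings end within about three weeks of training. The figures are Gaussian with complete data, while diminutives are tabulated as frequencies and may go to a generalised model; neither that nor missing sessions was simulated. Aim 2 is also labelled a test of preliminary effects, so an excess of a few points matters less than in a confirmatory trial.

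A second reply is that an unstructured matrix cannot simply be put into the model as written. That also stands: by step 6 the fit has no maximum, and the heterogeneous fallbacks share the fault.

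Neither reply supplies the missing rule. The plan states a 0.05 level and leaves the pattern open until the data are seen.

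**Conclusion.** The point holds conditionally. If post-post correlation exceeds pre-post correlation, choosing the pattern from the data puts change-from-pre contrasts at about 5–8% with AIC and 6–11% with BIC. The top of the range is for the mean of the post sessions under BIC with a smaller post SD. The size rests on an assumed post-post correlation, a borrowed pre-post correlation, complete Gaussian data and no home effect.

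Three stronger readings are tempting, and the documents do not support them:
- A reader might infer that the Aim 2 test as planned exceeds 5%. No primary test is named, the 3-df interaction stays at 4.5–6.5%, and there is no inflation if compound symmetry or AR(1) is true.
- A reader might infer that an unstructured matrix comes free. It costs about 1 power point when compound symmetry is true, and it needs the double use of baseline removed first.
- A reader might infer that it secures the 5% level. It removes this one source of error. A random home intercept cancels from change, so home variance in change is untouched (about 6.1% at an assumed ICC of 0.01).

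**What to change.** In this order, in Section II.C, Aim 2:

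1. Use baseline once. Either keep the pre session as a response and drop the baseline covariate, or keep the covariate and model only the three post sessions.
2. Name the primary contrast, for example one post session or the mean of the three.
3. Replace the covariance sentence with: *An unstructured within-CNA covariance (4×4 if the pre session is a response, 3×3 if it is a covariate) will be used, with Kenward-Roger standard errors and degrees of freedom. If it does not converge, heterogeneous Toeplitz and then heterogeneous compound symmetry will be used, in that order.*
4. If a generalised mixed model is used, pre-specify its CNA random-effects structure instead, because a residual matrix does not carry over directly.
5. State separately how nursing-home variance in change will be handled.

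Items 1 to 4 need only SAP wording: no new recordings, visits or participants. About 60 × 4 = 240 session records can support the ten parameters of a 4×4 matrix. The price is about 1 power point if compound symmetry is in fact true.

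### The stated 80% power for 0.74 to 0.76 SD depends on subject-level degrees of freedom; on the six randomised nursing homes it is about 57%, and the contrast is not named

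*Combined protocol and SAP*

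**What the plan says.** Section II.B describes a cluster randomised trial in six NHs: "These NHs will be randomly assigned to immediate feedback (n=3", with the other three as controls. Twelve certified nursing assistants (CNAs) are enrolled per NH, so that at least 30 per group complete.

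For Aim 2, section II.C says that 30 CNAs per group, on average ten per NH, "will achieve 80% power to detect a difference between the group means of 0.74 to 0.76 standard deviations". The inputs are an intracluster correlation (ICC) of 0.001 to 0.01 and a coefficient of variation (CV) of cluster size of 0.25. On the test it says: "A two-tailed t-test was used with a significant level of 0.05 and the degrees of freedom based on the number of subjects".

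The analysis is a linear or generalised linear mixed model with baseline use, group and session as fixed terms; the "interaction between intervention and session will be fitted as fixed effects". On the NHs: "To account for clustering, each NH will be fitted as a random effect". No df method is given, and no session, average or model term is named as the quantity that the power figure concerns. Section II.B speaks only in general of changes in diminutive use.

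On timing, section II.B says: "Immediate feedback NH CNAs will receive the app feedback at the end of each post- CHATO recording session". The Audio Recordings paragraph agrees: "The feedback group CNAs will receive automated feedback on elderspeak use after each post-CHATO recording session".

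**The concern.** There are two linked problems.

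First, the calculation inflates the variance for clustering but takes its critical value from the number of CNAs. The between-NH variance has to be estimated from six NHs, which leaves 2 × (3 − 1) = 4 df. The two-sided 5% critical value is then 2.78, not 2.00.

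Second, the figure is for an unspecified difference in means, while the model could deliver a single-session effect, an average or an interaction. The time 1 recording is made before any CNA has had feedback, so it should show no feedback effect, and any average that includes it is diluted.

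A null result would be read as coming from a trial with 80% power for about three quarters of an SD. The same figure could be carried into the design of the larger study that Aim 2 is meant to inform.

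**Working it through.** **Inputs (section II.C).** n = 30 per group; m = 10 per NH; CV = 0.25; ICC 0.001 paired with 0.74 SD, and ICC 0.01 paired with 0.76 SD; two-sided 0.05.

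**Step 1: design effect and noncentrality.** DE = 1 + ((1 + CV²)m − 1) × ICC = 1 + 9.625 × ICC, and ncp = d / √(2 × DE / 30).

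- ICC 0.001: DE = 1.0096; ncp = 0.74 / 0.2594 = 2.852.
- ICC 0.01: DE = 1.0963; ncp = 0.76 / 0.2703 = 2.811.

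**Step 2: the plan's own figure, then 4 df (noncentral t).**

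| df | Critical t | Power, 0.74 SD (ICC 0.001) | Power, 0.76 SD (ICC 0.01) | Difference for 80% power |
|---|---|---|---|---|
| 58 | 2.002 | 80.1% | 78.9% | 0.739 and 0.770 SD |
| 4 | 2.776 | 57.8% | 56.7% | 0.976 and 1.017 SD |

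The 58-df row reproduces the plan to within about 1 point, and a normal approximation gives 0.727 and 0.757 SD. So the arithmetic is sound and the df input is at fault. If all 12 enrolled CNAs per NH completed, 4 df would still give only about 65% and 63%.

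**Step 3: contrasts the model could deliver, on 4 df.** Assume an equal correlation r between any two sessions, baseline adjustment, and an NH component that averaging does not reduce. Then the variance of the difference is 2[ICC(1 + CV²)m + (1 − ICC)f] / 30, in single-session SD units.

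The documents give no r for diminutives. Section I.B reports for the earlier CHAT trial that "elderspeak declined from 34.6% (SD = 18.7) at baseline by 13.6 percentage points (SD = 20.00", and a change SD of 22.0 at 3 months. If SDs are equal over time, r = 1 − 20.0² / (2 × 18.7²) = 0.43, or 1 − 22.0² / (2 × 18.7²) = 0.31. These describe all elderspeak, so they are only indicative.

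| Contrast | f | Power at r = 0.43 (0.74 SD; 0.76 SD) | Range, r = 0 to 0.7 |
|---|---|---|---|
| One session | 1 − r² | 66.0%; 64.0% | 57–84% |
| Mean of three, equal effect | (1 + 2r)/3 − r² | 88.7%; 84.6% | 84–96% |
| Mean of three, no effect at time 1 (average 2d/3) | (1 + 2r)/3 − r² | 58.1%; 52.8% | 52–72% |
| Mean of times 2 and 3 | (1 + r)/2 − r² | 82.5%; 78.8% | 77–93% |

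Over r = 0.31 to 0.43, one session gives 60–66% and the mean of times 2 and 3 gives 77–83%. One session reaches 80% only if r is at least 0.66 (ICC 0.001) or 0.70 (ICC 0.01). A simulation on NH means at r = 0.43 agreed with the r = 0.43 column to within 1 point.

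**Step 4: type I error if the model's test also used 58 df.** This was simulated for a balanced REML fit with the NH variance truncated at zero. Null rejection is 3.8% at ICC 0.001 and 4.4% at 0.01. It rises to 6.5% at 0.05 and about 8% at 0.10, both assumed values above the plan's range.

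**The case against.** The plan discloses its df choice and its figure reproduces, so this is a choice of method and not a slip. Within the plan's ICC range, a 58-df mixed-model test does not inflate type I error. Simulated at the plan's two points, that test has about 73% power, a shortfall of 7 points and not 23. The 57% belongs to a t-test on NH means, which the plan does not propose. At these ICCs the NH variance is estimated as zero in 53% to 58% of trials. Power is then 44% to 45% if 4 df are kept and 59% to 60% if the df revert to 58, so a restated sentence need not match a REML analysis exactly. The outcome may need a generalised model, NHs may be added, and the trial is preliminary.

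Much of this is fair, and it limits the point. The 57% is not the power of the planned model, the type I concern is conditional, and handling of a zero NH variance should be specified. None of it restores the stated 80%. The 58-df mixed-model test falls short too, and its validity relies on a near-zero ICC, a quantity Aim 2 itself sets out to estimate. A test that reverts to 58 df lands close to the restated figure. A generalised model needs only an analogous small-sample correction. NHs are added only if too few CNAs complete, so a trial that recruits as planned has six.

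**Conclusion.** The concern holds. The stated 80% power for 0.74 to 0.76 SD is a property of subject-level df that six randomised NHs do not supply. On the plan's own inputs and 4 df, the same calculation gives about 57% power and needs 0.98 to 1.02 SD. That result needs no assumption beyond the documents, except that the comparison is tested on between-NH df.

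Whether the planned model reaches 80% is open. It depends on the contrast and on r, and the figures for both rest on an assumed equal correlation. At r = 0.43, including the pre-feedback time 1 session in the average moves power from 79–83% to 53–58%, if that session carries no effect. The correction should be made, but Aim 2 is exploratory and no confirmatory claim depends on it.

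**What to change.** In section II.C, Aim 2:

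1. Name the contrast that the power figure concerns (one post-training session, the mean of times 2 and 3, or the mean of all three) and say whether it is adjusted for baseline. Note that time 1 precedes any feedback.
2. Recompute on 4 df. If the single unadjusted comparison is kept, the sentence could read: *With three NHs per group, 10 CNAs per NH, ICC 0.001 to 0.01, CV 0.25 and 4 degrees of freedom (number of NHs minus 2), 30 CNAs per group give 80% power for an unadjusted single-session difference of 0.98 to 1.02 SD (about 57% at 0.74 to 0.76 SD).* If an adjusted or averaged contrast is chosen, state the assumed between-session correlation and show power over a range of it.
3. State that the group contrast is estimated by REML with Kenward-Roger or Satterthwaite df. Give the small-sample counterpart if a generalised model is used, and the df rule if the NH variance is estimated as zero.

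The cost is protocol wording only, with no added participants. The quoted power becomes less favourable for the current calculation, and an adjusted or averaged contrast needs an explicit correlation assumption.
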